#### 2.2.6.2 STUDY SUCCESS

The null hypothesis is that the probability of achieving Month 24 composite clinical success (CCS) for patients implanted with the Simplify® Disc device is no more than 0.10 smaller than the probability of ACDF control patients achieving Month 24 CCS. This study will be considered a success if the PS-quintile adjusted, multiple imputation based, 1-sided p-value for rejecting this null hypothesis is less than 0.05.

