It is assumed for the purpose of sample size analysis that at least 80% of the 116 evaluable ACDF controls, that is, N=93 will be remaining after the iterative PS sub classes determination and that the success rate will be 74.1% in the retained sample. It is possible that the effective sample size will be slightly higher since, as described below, multiple imputation will be used to address missing data from the prior study.

In order to have a sufficient size sample for safety profile evaluation, 150 investigational device patients will be enrolled. For the purpose of sample size evaluation, this value is reduced by 15% to account for loss-to-follow-up. It is further assumed that no more than 10% of the analysis set will be excluded based on design of the PS sub classes, reducing the evaluable sample size from 128 to 115.

The assumptions above imply an expected device group difference equal to equal to 7.3% for the primary endpoint. The study is designed to demonstrate non-inferiority using a non-inferiority margin equal to -10.0%.

If there were N=115 Simplify® Disc patients, then a “two-group large-sample normal approximation test of proportions with a one-sided 0.05 significance level will have 91% power to reject the null hypothesis that the test and the standard are not equivalent (the difference in proportions,  $\pi_1 - \pi_2$ , is -

0.10 or farther from zero in the same direction) in favor of the alternative hypothesis that the proportions in the two groups are equivalent, assuming that the expected difference in proportions is 0.073 and the proportion in the standard group is 0.741 [REDACTED]).

Thus, as long as the superiority margin between the Simplify® Disc and ADCF about the same as observed between Kineflex|C and ADCF, then N=115 patients included in the Simplify® Disc analysis set will result in adequate (i.e.,  $\geq 80\%$ ) statistical power. As noted above, this sample size is conservatively increased by 15% to account for potential loss-to-follow-up and by 10% to account from exclusions during the PS modeling. Therefore, the target prospective enrollment is N=150.

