#### 2.2.6.7 ADDRESSING MISSING OUTCOME DATA

Because of the availability of subject level data in controls that correspond to the subject level data to be collected in the prospective study, missing data will be addressed in the same fashion to how missing data would have been addressed in a randomized clinical trial. Multiple imputation will be used to impute missing final NDI in patients otherwise evaluable for primary CCS. For each of 20 imputed data sets, the primary PS stratified device group difference will be made resulting in a standard error for each. The final device group difference will be the average of the multiple imputed datasets and its standard error will account for both within (usual) and between imputation error.

In addition to multiple imputation, sensitivity analysis will be provided based on tipping point analyses. These are analyses in which all possible combinations of successes and failures are assumed for patients missing primary CCS and the fraction of scenarios in which the statistical conclusion changes is summarized. Best case and worst case, all missing success, and all missing failures scenarios will also be summarized.

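### The tipping-point summary (Section 2.2.6.7) is a fraction of undefined scenarios; its value depends on how they are counted, and it does not show where the conclusion tips.

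*Combined protocol and SAP*

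**What the plan says.** Section 2.2.6.7 makes multiple imputation the main method for missing data: "Multiple imputation will be used to impute missing final NDI in patients otherwise evaluable for primary CCS". It then adds a tipping-point analysis in which "all possible combinations of successes and failures are assumed for patients missing primary CCS", and the planned summary is that "the fraction of scenarios in which the statistical conclusion changes is summarized". The next sentence adds four named extremes: "Best case and worst case, all missing success, and all missing failures scenarios will also be summarized".

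The section does not say whether a scenario is a pair of success counts (one per arm), an assignment of success or failure to each patient, or a set of counts by propensity-score quintile. It does not say whether the conclusion in question is non-inferiority, superiority or both. It gives no weighting, no threshold for reading the fraction, and no commitment to show which combinations change the result.

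**The concern.** A fraction of scenarios is a probability under an unstated model. If every patient-level assignment counts equally, each missing patient in either arm is treated as an independent 50% chance of success. If every pair of counts is equal, 0 of 20 successes is as likely as 16 of 20. Neither matches the rates on which the trial is planned, and the plan chooses neither.

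A tipping-point analysis should let the reader see how far outcomes in patients with missing data must depart from those observed before the conclusion changes, and then judge whether that departure is credible. A single percentage hides this. It matters here because the controls come from an earlier trial, so the reasons for missing data may differ between arms, and because the readable text offers only this analysis and the four extremes as checks on the imputation.

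**Working it through.** **Inputs from the plan.** Section 2.2.6.2 requires that the "1-sided p-value for rejecting this null hypothesis is less than 0.05". Section 2.2.6.4 gives a "non-inferiority margin equal to -10.0" percent and assumes that "the success rate will be 74.1% in the retained sample". It adds an expected difference of 7.3 points, so the Simplify rate is 81.4%. The planned evaluable numbers are 115 Simplify and 93 ACDF.

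**Reproducing the plan's figure.** The plan gives none for the tipping-point analysis, so I checked the power with the same test:
- SE = √(0.814×0.186/115 + 0.741×0.259/93) = 0.0581.
- Power = Φ((0.073 + 0.10)/0.0581 − 1.645) = Φ(1.331) = 0.908, which agrees with the stated 91%.

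**Assumed numbers missing.** Simplify: 150 × 0.90 = 135 after propensity-score exclusions; 135 − 115 = 20. ACDF: 133 × 0.80 ≈ 106; 106 − 93 = 13. Observed successes, rounded from the planning rates: 94/115 and 69/93.

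**Enumeration.** Let a be the successes among the 20 missing Simplify patients and b those among the 13 missing ACDF patients. Then p1 = (94 + a)/135 and p2 = (69 + b)/106. Non-inferiority holds if (p1 − p2 + 0.10)/√(p1(1−p1)/135 + p2(1−p2)/106) > 1.645. This crude test stands in for the quintile-adjusted one.
- Count pairs: 21 × 14 = 294. Non-inferiority is lost in 45, or 15.3%.
- Patient-level assignments: 2^33, about 8.6 billion, obtained by weighting each pair by C(20,a)·C(13,b). Non-inferiority is lost in 0.23%.

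**Other cases** (count pairs against patient-level assignments):

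| Observed and missing | Count pairs | Patient level |
|---|---|---|
| 104/128 + 22 vs 86/116 + 17 (no exclusions) | 55/414 = 13.3% | 0.05% |
| 94/115 + 20 vs 69/93 + 13 | 45/294 = 15.3% | 0.23% |
| 90/115 + 20 vs 69/93 + 13 | 29.6% | 8.1% |
| 88/115 + 20 vs 69/93 + 13 | 38.8% | 23.6% |
| 86/115 + 20 vs 69/93 + 13 | 48.3% | 47.3% |

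In the two planning cases the figures differ by a factor of roughly 65 to 250. For superiority (margin zero, not met at 94/115), the conclusion changes in 85/294 = 28.9% of pairs or 7.7% of assignments.

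**What the boundary shows.** At 94/115, non-inferiority holds whatever happens to the missing Simplify patients if at most 5 of 13 missing ACDF patients succeed. Beyond that, it needs:
- at least 2 of 20 Simplify successes when 6 of 13 ACDF patients succeed;
- at least 6 of 20 when 10 of 13 succeed (z = 1.547 with 5 successes, 1.684 with 6);
- at least 10 of 20 when all 13 succeed.

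**Where the fraction can mislead.** At 88/115 (76.5%), patient-level counting says that about 76% of scenarios keep non-inferiority. Yet with 10 of 13 missing controls succeeding (77%, close to the planned 74.1%), it is lost at 11 of 20 Simplify successes (55%). A reader can judge whether 55% is credible for patients lost to follow-up; the fraction does not allow that judgement.

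**The four extremes.** At 94/115 the worst case fails and the other three pass, which does not say how near the boundary is.

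**The case against.** The strongest reply is that this is a matter of definition and display in a secondary analysis. No decision rule depends on the fraction, and nothing in Section 2.2.6.7 prevents the sponsor from showing the grid. The four extremes do not depend on the counting unit, and if the worst case passes, robustness is settled. The largest gap between the two counts arises where the result is robust: at 94/115 the conclusion tips only if at most 25% of missing Simplify patients succeed while 77% of missing controls do. Near the boundary the counts converge. All of this is right, and it limits the point to a sensitivity analysis. It does not make the fraction interpretable, as the 88/115 case shows.

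A second objection also stands. In the stratified analysis one pair of counts may pass or fail depending on which quintiles hold the successes. With missing patients spread as 4 per quintile (Simplify) and 3, 3, 3, 2, 2 (ACDF), about 2 of 294 cells are ambiguous if quintiles are of equal size. The number rises to about 61 with moderately unbalanced quintiles (Simplify 17 to 37, ACDF 31 down to 12) and about 120 with strongly unbalanced ones (12 to 42 and 36 down to 7). These layouts are assumptions, and the counts shift somewhat with the stratum weights. A simple grid therefore needs an allocation rule.

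Three stronger readings are tempting and unsupported:
- A reader might infer that enumerating patient-level assignments is infeasible. It is not: the test depends only on counts, so assignments collapse to weighted counts. Even by quintile, the layout above gives 5^5 × 4^3 × 3^2 = 1,800,000 combinations, which is easily computed.
- A reader might infer that the plan cannot address non-random missingness. The planned runs contain the boundary and the extremes are reported; the plan just does not commit to showing the boundary.
- A reader might take 15% missing as a forecast. Section 2.2.6.4 presents it as a conservative allowance.

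**Conclusion.** The point holds as a defect in how a sensitivity analysis is defined and summarized. The planned fraction has no single value: 15.3% or 0.23% from the same data at planning values. It weights scenarios by an arbitrary implicit model and does not locate the tipping boundary; the four extremes bound the result without locating it either. The primary test and the success criterion in Section 2.2.6.2 are untouched.

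The figures rest on success counts rounded from planning rates, on 20 and 13 missing outcomes derived from the plan's allowances, and on an unstratified Wald test. They show the size of the ambiguity. A reader should not take 5 of 20 as this trial's boundary, because actual missingness and quintile layout are unknown. Sections 2.2.6.9 and 2.2.6.10 are redacted, so related detail there cannot be excluded; the readable missing-data section has none.

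**What to change.** In Section 2.2.6.7, replace the fraction with a tipping-point grid, or keep the fraction as a supplement with the scenario unit defined. The grid should:
- cross the number of successes among missing Simplify patients with the number among missing ACDF patients;
- mark where the stratified non-inferiority conclusion changes and, separately, where the superiority conclusion of Section 2.2.6.6 changes;
- mark the point at which missing patients succeed at their arm's observed rate;
- state how successes are allocated across propensity-score quintiles, or else label each cell as always passing, always failing or dependent on allocation.

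Keep the four extreme scenarios.

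The cost is SAP wording, an allocation rule and one more figure or table. The scenarios are already planned, so no new data are needed; the allocation rule is the only real added work.

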#### 2.2.6.8 PLANS TO ASSESS SITE POOLABILITY

Assessment of site poolability for the likelihood of achieving primary CCS will be performed for sites enrolling patients into the Simplify® Disc group. This assessment will involve estimating the parameters of a random effects meta-analysis. The observed site-specific success rates will be subjected to an arcsine in order to remove the dependence of within site variance and expected success rate (Freeman and Tukey, 1950). This permits application of the DerSimonian and Laird random effects meta-analysis approach. The R function *metaprop* in the R package *meta* deals

---

 Freeman MF & Tukey JW. Transformations related to the angular and the square root. *Annals of Mathematical Statistics* 1950, 21, 607–611.

implements DerSimonian and Laird random effects meta-analysis using an arcsine transformations and so this software will be used. This package requires the numbers of events and total sample size for each study to be provided as arrays.

The transformed success probabilities are assumed to follow a normal distribution with mean  $\mu$  and variance  $\tau^2$ . The magnitude of site-to-site variability in primary CCS for the Simplify® Disc will be quantified using the  $I^2$  statistics (Higgins et al 2004).  $I^2$  is the fraction of  $\tau^2$  that is due to effect size heterogeneity, as opposed to sampling variance. Higgins *et al* indicate that, “A naive categorization of values for  $I^2$  would not be appropriate for all circumstances, although we would tentatively assign adjectives of low, moderate, and high to  $I^2$  values of 25%, 50%, and 75%”.

Therefore, the key quantitative assessment of whether or not site-to-site variability is important will involve the comparison of the observed  $I^2$  value for the prospective study to the above guidelines. In addition to  $I^2$ , the statistical significance of the site-to-site variability will be determined using the Q statistic with degrees-of-freedom equal to the number of sites minus 1. Sites contributing less than 6 patients will be combined prior these analyses.

2.2.6.9 [REDACTED]

[REDACTED]

[REDACTED]

- [REDACTED]
- [REDACTED]
- [REDACTED]
- [REDACTED]
- [REDACTED]
- [REDACTED]

---

29 DerSimonian R and Laird NM. Meta-analysis in clinical trials. *Journal of Controlled Clinical Trials*, 1986; 7:177-188.  

[Redacted]

- [Redacted]
- [Redacted]
- [Redacted]
- [Redacted]

[Redacted]

[Redacted]

2.2.6.10 [Redacted]

[Redacted]

[Redacted]

[Redacted]

[Redacted]

[Redacted]

[Redacted]

[Redacted]

[Redacted]

[Redacted]

[Redacted]

[REDACTED]	[REDACTED]
[REDACTED]	[REDACTED]
[REDACTED]	[REDACTED]
[REDACTED]	[REDACTED]
[REDACTED]	[REDACTED]
[REDACTED]	[REDACTED]
[REDACTED]	[REDACTED]
[REDACTED]	[REDACTED]

2.2.6.11 SECONDARY ENDPOINTS

Secondary endpoints include:

- Clinically significant improvement in one or more radicular symptoms or myelopathy at 24 months compared to baseline for the investigational Simplify® Disc and 24 months compared to baseline for the control ACDF. The data collected will reflect the number of patients who improved (numbers will be stratified to reflect clinical improvement), who remain unchanged, and who deteriorated at each study time point. These endpoints will be graded and defined as follows:
  - A visual analog scale (VAS) will be used to evaluate each of the following pain locations:
    - Neck and arm pain (to allow comparison to ACDF control)
    - Neck pain
    - Left arm pain;
    - Right arm pain;

Changes of at least 20 mm on a 100 mm scale will be regarded as clinically significant.

- Motor status - A change of one or more grade levels in muscle strength will be regarded as clinically significant.

- Sensory status - Sensation will be graded as normal or abnormal (diminished or absent). Any changes from abnormal to normal or absent to diminished will be regarded as clinically significant improvement..
- Time to recovery (time to first 15-point NDI improvement).
- Disc height at 24 months compared to baseline for the investigational Simplify® Disc and at 24 months compared to baseline for the control ACDF, as measured by standard lateral radiograph (spot film, distance of 6 feet, centered at C5 with patient upright).
- Adjacent level deterioration at 24 months compared to baseline for the investigational Simplify® Disc and at 24 months compared to baseline for the control ACDF.
- Displacement or migration of the device; only changes of > 3 mm will be considered significant due to the margin of error in radiographic determination of displacement distances.
- Treatment satisfaction at 24 months for the investigational Simplify® Disc and at 24 months for the control ACDF.
- Health Survey (SF-12v2) for the investigational Simplify® Disc at 24 months compared to baseline.
- Dysphagia Handicap Index (DHI scale) for the investigational Simplify® Disc at 24 months compared to baseline.
- Facet deterioration for the investigational Simplify® Disc at 24 months compared to baseline..
- Results at 24 months for the investigational Simplify® Disc and at 24 months for the control ACDF will also be categorized by the physician according to Odom's Criteria, as described below.

Excellent	Improvement in most (at least 80%) of the preoperative signs and symptoms, with little deterioration (not more than 10%)
Good	Improvement in some (at least 70%) of the preoperative signs and symptoms, with some deterioration (not more than 15%)
Fair	Improvement in half (at least 50%) of the preoperative signs and symptoms, with some deterioration (not more than 20%)
Poor	Improvement in few (less than 50%) of the preoperative signs and symptoms, or significant deterioration (more than 20%)

---

 Hacker *et al.*, *supra* note 7.

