##### **2.2.5.2 PRE-TREATMENT EVALUATIONS AND DATA COLLECTION**

Pre-treatment evaluations and data collection will include:

- Radiographic studies for verification of DDD;
- AP and lateral X-rays (plain films);
- Flexion-extension X-rays (used to determine range of motion);
- Lateral bending films;
- MRI or CT (investigational group only)
- Radiographic core lab evaluations;
- Dysphagia Handicap Index (investigational group only);
- Study related medical history and physical examination;
- DXA (if indicated as described in Section 2.2.3.2);
- NDI assessment;
- SF-12v2 Health Survey (investigational group only);
- VAS pain assessments (neck and arm; neck, left arm and right arm (investigational group only));
- Neurologic evaluation;
- Study related medication history and
- Work status.

Radiographic studies used for verification of DDD, DEXA scans and baseline MRI or CT may be taken up to 6 months prior to the pre-treatment evaluation. Flexion/extension X-rays and AP & lateral X-rays and lateral bending X-rays must be taken no sooner than 90 days prior to the pre-treatment evaluation. *All other pre-treatment measurements* must be done no sooner than 30 days prior to the pre-treatment evaluation.

The neurologic evaluation will include a motor and sensory assessment, reflex responses and the determination of the presence or absence of dysphagia, dysphonia, clumsiness, foot drop, atrophy, cramping, muscle spasms, numbness and gait abnormality.

For the purposes of this clinical study, only medications taken or administered for the following will be recorded on the Case Report Form:

---

- Pain (any type);
- Inflammation (any type);
- Muscle relaxation;
- Numbness &/or tingling;
- Hormonal replacement therapy and
- Other medications related to or given for the subject's spinal condition.

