#### 2.2.5.4.3 Follow-Up Evaluations and Data Collection

Follow-up evaluations at 6 weeks will include:

- AP and lateral X-rays (plain films);
- Dysphagia Handicap Index (investigational group only);
- NDI assessment;
- VAS pain assessments (neck and arm; neck, left arm and right arm (investigational group only));
- Odom's criteria determination;
- Neurologic evaluation;
- Study-related medications; and
- Adverse events as defined by Section 2.2.6.1 and Section 2.2.7 of this protocol.
- [REDACTED]

Follow-up evaluations at 3 and 6 months will include:

- AP and lateral X-rays (plain films);
- Flexion-extension X-rays (used to determine range of motion);
- Lateral bending films (starting at 6 months);
- Radiographic core lab evaluations;
- Dysphagia Handicap Index (investigational group only);
- NDI assessment;
- SF-12v2 Health Survey (6 months for investigational group only);
- VAS pain assessments (neck and arm; neck, left arm and right arm (investigational group only));
- Odom's criteria determination;
- Neurologic evaluation;
- Study-related medications;
- Work status and
- Adverse events as defined by Section 2.2.6.1 and Section 2.2.7 of this protocol.
- [REDACTED]

Follow-up evaluations at 12 and 24 months will include:

- AP and lateral X-rays (plain films);

- Flexion-extension X-rays (used to determine range of motion);
- Lateral bending films;
- MRI assessment (investigational group only at 24 month);
- Radiographic core lab evaluations;
- Dysphagia Handicap Index (investigational group only);
- NDI assessment;
- SF-12v2 Health Survey (investigational group only);
- VAS pain assessments (neck and arm; neck, left arm and right arm (investigational group only));
- Odom's Criteria determination;
- Neurologic evaluation;
- Study related medication status;
- Work status;
- Patient satisfaction assessment and
- Adverse events as defined by Section 2.2.6.1 and Section 2.2.7 of this protocol.
- [REDACTED]

Subjects who complete their 24 month visit prior to the last study subject's completion of the 24 month visit will continue to be followed annually until the last subject enrolled has completed the 24 month evaluation. However, for the purpose of primary safety and efficacy evaluations, the study completion/ termination assessment will be made at 24 months postoperatively, or at an earlier time point if the subject withdraws or is withdrawn from the study.

Follow-up evaluations annually after 24 months will include:

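### Does the secondary endpoint on radicular symptoms give Simplify more ways to count as improved, because three of its four pain scales were not collected in the ACDF control?

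*Combined protocol and SAP*

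**What the plan says.** Section 2.2.6.11 of the combined protocol and SAP lists "Clinically significant improvement in one or more radicular symptoms or myelopathy at 24 months compared to baseline" for Simplify, and likewise "24 months compared to baseline for the control ACDF". Patients are to be counted as improved, as those "who remain unchanged, and who deteriorated at each study time point". The section continues: "These endpoints will be graded and defined as follows". Under that line come:

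- four VAS locations: combined neck and arm, neck, left arm, right arm. The first carries the note "Neck and arm pain (to allow comparison to ACDF control". One threshold serves all four: "Changes of at least 20 mm on a 100 mm scale will be regarded as clinically significant";
- motor status, where a change of one strength grade or more counts;
- sensory status, with its own definition of improvement.

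The collection schedules show which scales exist in each arm. Section 2.2.5.2 (baseline) has "VAS pain assessments (neck and arm; neck, left arm and right arm (investigational group only", and section 2.2.5.4.3 (follow-up, including month 24) repeats "neck, left arm and right arm (investigational group only". The neurologic evaluation, which supplies motor and sensory status, carries no such restriction.

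**The concern.** Read literally, the endpoint is an any-of rule applied to both arms: a patient succeeds by improving on at least one listed symptom. An any-of rate cannot fall when a component is added and will normally rise. Scoring Simplify patients on six components and controls on three would therefore produce a gap in Simplify's favour with no treatment effect at all. The control is historical, so the missing scales cannot be collected now, and propensity score subclassification balances baseline covariates but does nothing about an outcome scored on different instruments. At stake is a misleading statement of pain or neurologic benefit in a secondary result. The same imbalance would raise Simplify's count of deteriorated patients.

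**Working it through.** The documents give no rate, power or test for this endpoint, so there is no stated figure to reproduce. The check is a count of components, an illustration of what the pooled reading could do, and a reading of the text.

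**Components per arm (sections 2.2.5.2, 2.2.5.4.3, 2.2.6.11)**

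| Component | Simplify | ACDF |
|---|---|---|
| VAS neck and arm combined | yes | yes |
| VAS neck | yes | no |
| VAS left arm | yes | no |
| VAS right arm | yes | no |
| Motor status | yes | yes |
| Sensory status | yes | yes |
| Total | 6 | 3 |

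**Pooled reading, no true device effect.** Every probability and correlation here is an assumption. Let p be the chance of a 20 mm improvement on any one VAS, r the correlation between the VAS changes, and s the chance of improving on motor or sensory status, equal in both arms and independent of VAS. Let A be the chance of improving on at least one of the VAS scales available in the arm. The any-of rate is 1 − (1 − A)(1 − s).

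Take p = 0.7, r = 0.7, s = 0.3.
- ACDF, one VAS: A = 0.70, rate = 1 − 0.30 × 0.70 = 0.790.
- Simplify, four VAS: A = 0.882 by simulation, rate = 1 − 0.118 × 0.70 = 0.917. The gap is about 12.7 points.
- Simplify, three VAS (only one arm symptomatic): A = 0.855, rate = 1 − 0.145 × 0.70 = 0.899. The gap is about 10.9 points.

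Over p from 0.5 to 0.8, r from 0.5 to 0.9 and s of 0, 0.3 or 0.5, the gap runs from about 4 to 30 points. If a one-sided 5% test were run at the planning sizes in section 2.2.6.4 (115 and 93), its false-positive rate would be about 24% to over 99%.

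**Sensitivity to the equal-chance assumption.** That grid gives each separate scale the same chance of improving as the combined one. Section 2.2.3.1 admits patients with symptoms in the neck, the arm or both, and a patient with little baseline pain at a site cannot improve by 20 mm there. I repeated the simulation (400,000 draws) with two extra VAS scales, motor and sensory improvement at 0.3 each, and correlations of 0.3 outside the VAS block:

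| Combined VAS | Each separate VAS | r | ACDF | Simplify | Gap (points) |
|---|---|---|---|---|---|
| 0.70 | 0.70 | 0.60 | 79.5% | 90.7% | 11.2 |
| 0.70 | 0.70 | 0.95 | 79.3% | 83.2% | about 4 |
| 0.70 | 0.60 | 0.70 | 79.4% | 86.2% | 6.8 |
| 0.80 | 0.50 | 0.90 | 85.7% | 85.9% | 0.2 |

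The direction is fixed; the size is not. Plausible inputs give anything from almost nothing to a large gap.

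**Does the plan call for the pooled reading?** Four features of section 2.2.6.11 point away from it.
1. The combined VAS is labelled as the scale for comparison with the control. That label has little purpose if all four scales feed the comparison.
2. The lead-in refers to endpoints in the plural, and VAS is applied to each location in turn.
3. VAS, motor and sensory status each have their own criterion for change.
4. Improved, unchanged and deteriorated are mutually exclusive on one scale. Under an any-of composite a patient could be both improved and deteriorated, and the visible text has no rule for that.

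With between-arm results limited to the shared components, each arm has three and the artificial gap is 0 by construction.

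**The case for a change.** The strongest reply is that the label on the combined scale explains why it was kept but does not say that the one-or-more count is limited to it. All four locations sit under an endpoint that names both arms. The same section states SF-12v2, the Dysphagia Handicap Index and facet deterioration for Simplify alone, so the authors knew how to mark a single-arm result and did not do so within this rule. Section 2.2.6.3 rests the comparability of the primary endpoint on components evaluated alike in both studies, and one sentence would extend that standard here. Even untested rates shown side by side could mislead.

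Much of this stands. The wording is ambiguous, one of its readings favours the device, and a clarifying sentence would cost little. What does not stand is that the plan prescribes the unfair comparison. The single-arm restriction on the three extra scales is stated in the collection schedules, and the shared scale is identified in the endpoint definition itself. Sections 2.2.6.9 and 2.2.6.10 are blacked out, so the absence of an explicit scoring rule cannot be counted against the plan.

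**Conclusion.** No change is needed: this is a gap that analysts fill sensibly. The imbalance in collected scales is real, six components against three, and pooling all of them would favour Simplify on improvement and count against it on deterioration. The more natural reading compares the arms on combined neck-and-arm VAS, motor status and sensory status and reports the other three scales for Simplify alone, which removes the artificial difference. An analyst could hardly do otherwise, since the control data hold no values for those three scales.

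Little depends on the point. Study success (section 2.2.6.2) rests on month 24 composite clinical success alone, and the superiority section (2.2.6.6) names no secondary endpoint. No between-arm test, margin or alpha for this endpoint appears in the visible text. The possible size under the pooled reading, near 0 to about 30 points, rests wholly on assumed improvement rates and correlations and on a scoring rule that the plan does not state.
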